| LG1 | Received speech therapy in last 6 months | Categorical (binary) |

¹ The date variables will be used to calculate length of stay, a continuous variable

² The date variables for MP1 will be used to calculate duration of treatment etc; likely continuous variables

| | | |
|------|---|-----------------------|
| LG2 | How many weeks of speech therapy? | Discrete |
| LG3 | Days per week of speech therapy? | Discrete |
| LG4 | Hours per day of speech therapy? | Continuous |
| LG5 | Percentage of sessions due to ear-related problems | Continuous |
| LG6 | Had out of pocket costs for speech therapy? | Categorical (binary) |
| LG7 | How much out of pocket per month? | Continuous |
| PSI1 | Received psychological therapy in last 6 months | Categorical (binary) |
| PSI2 | How many weeks of psychological therapy? | Discrete |
| PSI3 | Days per week of psychological therapy? | Discrete |
| PSI4 | Hours per day of psychological therapy? | Continuous |
| PSI5 | What % of these sessions were due to ear problems | Binomial (proportion) |
| PSI6 | Had out of pocket costs for psychological therapy? | Categorical (binary) |
| PSI7 | How much out of pocket per month? | Continuous |
| SC1 | How many times attending adult day care in last 6 months? | Discrete |
| SC2 | Is the stay due to hearing difficulties? | Categorical (nominal) |
| SC3 | Out of pocket costs for adult day care? | Categorical (binary) |
| SC4 | Out of pocket cost per month for adult day care | Continuous |
| RES1 | Lived in a residential care home in the last 6 months | Categorical (binary) |
| RES2 | How many months in residential care in last 6 months | Continuous |
| RES3 | Is residential care stay related to hearing difficulties? | Categorical (nominal) |
| RES4 | Out of pocket expenses in residential care home? | Categorical (binary) |
| RES5 | How much out of pocket per month? | Continuous |
| AD1 | Hope help/social services in the last 6 months | Categorical (binary) |
| AD2 | How many months home help/social services in last 6 months | Discrete |
| AD3 | How many days/week home help/social services in last 6 months | Discrete |
| AD4 | How many hours per day home help/social services in last 6 months | Continuous |
| AD5 | Is home help/social services related to hearing? | Categorical (nominal) |
| AD6 | Out of pocket expenses for home help/social services? | Categorical (binary) |
| AD7 | How much out of pocket per month? | Continuous |
| CI1 | Limited in daily activities due to disability/health problem in last 6 months | Categorical (nominal) |
| CI2 | What percentage of health or disability problems relates to ear problems | Continuous |
| CI3 | Hours per week people help you with your needs | Continuous |

Other data:

The forms also collect information on:

- Gender (categorical; binary)
- Date of birth
- Inclusion/exclusion criteria
- Hearing, device and medical histories (a combination of categorical and continuous variables)

7. Statistical Analysis Plan

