Exclusion criteria:	
 • Significantly/severely dependent or fragile • Unable to provide consent personally • Unable to complete questionnaires for self-assessment independently • Unilateral hearing loss • Sequential and simultaneous bilateral cochlear implant recipients • Ossification or other cochlear anomalies preventing full electrode insertion • Retro cochlear or central origins of hearing impairment. • Significant comorbidities preventing study participation (e.g. blindness, immobility or in a wheel chair, severe aphasia,.) • Medical contraindications to surgery • Clinic Standard fail criteria for CI candidacy in regards to chronic depression, dementia, and cognitive disorders. • Unrealistic expectations on the part of the subject, regarding the possible benefits, risks and limitations that are inherent to the procedure and prosthetic device. 				
Primary objective:	To evaluate the change in health related quality of life following CI treatment in the elderly individuals by using the generic Health Utilities Index Mark III (HUI 3) tool prospectively.				
Secondary objectives:	To evaluate the impact of CI treatment in the elderly on the domains that have an impact on healthy aging and overall well-being such as hearing ability, dependency, cognition, falls, depression.				
Tertiary objective:	To identify healthcare resource utilisation that is impacted by CI treatment versus no treatment.				
Treatment and follow up schedule: Q - questionnaire A - standard audiological measure G- standard geriatric measure NA -not Applicable		Q/A.	Pre1 Visit 1	Post 1 Visit 2	Post 2 Visit 3
Patient Profile	Q	X	X		X
Healthcare resources	Q	X	X		X
CAP-II	Q	X	X		X
L-IADL	Q	X	X		X
Data Logging	A	NA	X		X
HUI3	Q	X	X		X
GDS-15	Q	X	X		X
HHIE-S	Q	X	X		X
SSQ	Q	X	X		X
PTA	A	X	X		X
SFT	A	X	X		X
Speech in Quiet	A	X	X		X
Speech in Noise	A	X	X		X
MMSE	G	X	X		X
DSST	G	X	X		X
TRAIL B	G	X	X		X
De Jong Loneliness scale	Q	X	X		X
TUG	G	X	X		X

Primary endpoints:	Change in HUI3 multi-attribute index scores preimplant to postimplant at 12 and 18 months post surgery.

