7.1 Study Objectives

1. To evaluate the change in health related quality of life following CI treatment in elderly individuals by using the generic Health Utilities Index Mark III (HUI 3) assessment scale prospectively.
2. To evaluate the impact of CI treatment on the domains that have impact on overall well-being and healthy aging in the elderly such as :
 - a) hearing ability and communication
 - b) dependency
 - c) cognition
 - d) falls
 - e) depression/mood
3. To identify the changes in healthcare resource utilisation following CI treatment compared to preimplant.

The hypotheses:

Primary hypothesis

CI implant treatment significantly improves **the overall health related quality of life** of elderly individuals compared to their preimplant condition as measured on the HUI-3.

Secondary hypothesis

CI treatment in the elderly significantly impacts the healthy aging domains and therefore overall well-being in addition to hearing function compared to the preimplant condition as measured on clinically standard evaluation tools in the geriatric and audiological fields.

Tertiary hypothesis

CI treatment has the potential to create cost savings from the perspective of health care payer(s), health care provider(s) and society, by reducing health care resource utilisation for bilaterally severe to profound hearing impaired adults over 60 years of age, post implant compared to their preimplant status.

8 Design of the observational study

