8.4 End-points

Primary end-point

Change in overall health related quality of life via comparison of HUI3 multi-attribute utility scores at:

- **Post1** implant Visit compared to **Pre1** implant Visit
- **Post2** implant Visit compared to **Post1** implant Visit
- **Post2** implant Visit compared to **Pre1** implant Visit

Secondary end-points:

Change in scores on battery of evaluation tools for health related domains and overall well-being on each of the following:

MMSE, DSST & Trail B (Cognition); TUG (falls); GDS-15 (depression); iADL (independency); HHIE-S (hearing handicap); SSQ (hearing & communication ability); CAP-II (capabilities of audition); De Jong Loneliness Scale, Speech recognition tests in Quiet (daily hearing function); Speech recognition tests in Noise (daily hearing function); Consistent daily use of CI via automatic data logging (hrs/day and listening environments).

- **Post1** implant Visit compared to **Pre1** implant Visit
- **Post2** implant Visit compared to **Post1** implant Visit
- **Post2** implant Visit compared to **Pre1** implant Visit

Tertiary end point:

Changes in healthcare resource utilisation with CI treatment compared to preimplant, collected at each test interval, i.e., Pre 1, Post1 and Post 2 will be compared. Each assessment will reflect a 6 month period immediately before assessment. Data reviewed for this measure will be obtained from the customized HRU questionnaire completed by the clinician on behalf of the subject (data sources available for use will be in accordance with regional guidelines).

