8.8 Monitoring Plan

The monitoring schedule and documents viewed are detailed in a separate document *“Monitoring Plan”*.

9 Statistical Considerations

For primary, secondary and tertiary study objectives an Intra subject endpoint comparison is used: All pairwise comparisons are of interest i.e. preimplant to 12 months postimplant, preimplant to 18 months postimplant, and the change from 12 to 18 months.

The power analysis applied for the study design was based on an available data set (n= 67, Cochlear-IROS data) of repeated measures on the HUI3, collected for elderly CI-patients, at preimplant and 12 months post implant intervals. The HUI 3 will serve as the primary outcome measure for this study to measure the added health utility gain for the multi- attribute health status from preimplant (@ \leq 2 months first activation) to the postimplant (@ 12 months post activation) interval in a population of implanted 60+ year olds.

The minimum clinically important change over two intervals for the HUI3 is 0.03 units on a scale of 0 representing poor health and 1.0 representing full health.

The power calculations were performed using the free package G*Power 3.1 by a consultant statistician at the Macquarie Sydney University.

The differences observed for the implanted elderly population in the existing Cochlear IROS dataset demonstrated a mean change = 0.165 at 95% confidence interval, with a range of 0.109 to 0.221 and a non-normal distribution for the cohort of 67 implanted elderly recipients over the age of 60 years examined.

Using this information to estimate the sample size required for significant changes on the HUI3 multi attribute score, *for intra subject comparisons of endpoints*, aiming for a change of \geq 0.10 units between the two test intervals, and a power of 90% and using a two-side paired t-test to calculate the 5% significance level, a sample of N=68 is required for the multi-attribute health utility. For comparison of changes in self ratings individual health domains of the HUI3, aiming for a power of 80% a sample of N=100 is required.

Study statistical analysis plan is available as separate document.

10 Data Management

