The aim, as described in the protocol, is to provide transparent and comparable medical evidence that can support health care policy makers to take informed decisions on the provision of health services for the treatment of hearing loss. A brief summary of the protocol follows.

3. Objectives of the Study

The primary objective is to evaluate the change in health-related quality of life following CI treatment by using the generic Health Utilities Index Mark III (HUI 3) multi-attribute index score. All pairwise comparisons are of interest i.e. preimplant to 12 months postimplant, preimplant to 18 months postimplant, and the change from 12 to 18 months.

A secondary objective involves evaluating the impact of CI treatment in the elderly on domains that may be associated with healthy aging and overall well-being such as

- hearing ability (using the Capabilities of Auditory Performance (CAP-II) test, the Speech Spatial and Qualities (SSQ) questionnaire, the Hearing Handicap Inventory for the Elderly Scale (HHIE-S), speech recognition tests in the quiet and in noise, pure tone audiometry (PTA) and sound field thresholds (SFT))
- independence (using the Lawton-instrumental Activities of Daily Living (L-iADL) tool)
- cognition (using the Mini Mental State Examination (MMSE) score, the Digit Symbol Substitution (DSST) test and the Trail Making Test version B (Trail B))
- falls (using the Timed Up and Go test (TUG))
- depression (using the Geriatric Depression Scale-15 (GDS-15), and the De Jong Loneliness Scale)
- CI usage measures.

All pairwise comparisons between time points, as defined above, are of interest here also.

A tertiary objective is to identify healthcare resource utilisation that is impacted by comparing costs post CI treatment with those prior to treatment.

For all of these objectives, interest is also in whether various demographic variables are associated with the change in outcome scores observed.

In summary:

Primary hypothesis

CI treatment significantly improves the overall health related quality of life of elderly individuals compared to their pre-implant condition (and again from 12 to 18 months following surgery) as measured by the HUI3 multi-attribute score.

Secondary hypothesis

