CI treatment significantly impacts healthy aging domains and wellbeing of elderly individuals compared to their pre-implant condition (and again from 12 to 18 months following surgery) as measured by clinically standard evaluation tools in the geriatric and audiological fields (as described above)

Tertiary hypothesis

CI treatment significantly reduces healthcare resource utilisation in elderly individuals over time.

Other hypotheses

There are covariates associated with the change in health-related quality of life and other healthy aging domains and related well-being.

4. Study Design

The study is a prospective observational longitudinal study performed to evaluate the benefits for overall health following CI treatment in the elderly population treated in routine clinical practice. Multiple centres are included in the study

Implantation with commercially available cochlear implant devices (i.e. products approved for market release) available for routine clinical treatment of deafness in all ages in collaborating investigator clinic sites is made as part of the study and no additional interventions are applied.

Change in outcome scores for various standard assessment tools and health domains post CI treatment compared to the pre-implant status are made using participants as their own controls. All questionnaires of interest are administered at each visit (up to 2 months pre-implant, 12 months post-implant [+/- 1 month] and 18 months post-implant [+/- 1 month]).

Whilst a recommended evaluation schedule is provided, participating clinics may select the optional evaluation measures they wish to use for their patients from the tools made available on the study specific electronic platform at baseline registration of each patient.

Participating in the study is voluntary and the participant is free to electively cease participation in the registry at any time. To be included in the study, participants must meet all local and study specific inclusion criteria and have none of the exclusion criteria. Participants remain in the study for a period of up to 2 years.

5. Sample size

Assuming that a paired t-test of the change in HUI3 multi attribute score from pre-implant to 12 or pre-implant to 18 months following implantation is of interest, then with 90% power and a 5% level of significance a change of 0.1 with standard deviation of change equal to 0.25, would require 68 participants.

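### The SAP's primary hypothesis adds a second significant HUI3 gain from 12 to 18 months that the protocol's hypothesis and synopsis do not claim, so a maintained benefit would leave it, read literally, unconfirmed

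*SAP*

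**What the plan says.** The primary claim is stated in several places, and they differ.

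- **Protocol 7.1, primary hypothesis:** improvement in quality of life "of elderly individuals compared to their preimplant condition as measured on the HUI-3". It makes no claim about the interval between the two post-implant visits.
- **Protocol synopsis, primary endpoint:** "Change in HUI3 multi-attribute index scores preimplant to postimplant at 12 and 18 months post surgery", that is, two contrasts against preimplant.
- **Protocol 8.4, primary end-point:** "Change in overall health related quality of life via comparison of HUI3 multi-attribute utility scores at" three visit pairs, one of which is Post2 against Post1.
- **Protocol 9:** interest in every pair, "preimplant to 12 months postimplant, preimplant to 18 months postimplant, and the change from 12 to 18 months". No direction is given for the last one.
- **SAP 3, primary hypothesis:** significant improvement over the pre-implant condition "and again from 12 to 18 months following surgery) as measured by the HUI3 multi-attribute score".

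SAP 5 gives its planning inputs for a paired test of the change "from pre-implant to 12 or pre-implant to 18 months following implantation is of interest": "a change of 0.1 with standard deviation of change equal to 0.25, would require 68 participants". It then divides the significance level by three, because all pairs are of interest, and arrives at 88. Neither document gives an expected change or an SD for 12 to 18 months. Neither says which contrasts must be significant for the primary hypothesis to count as confirmed.

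**The concern.** Listing the 12-to-18-month change as a comparison is one thing; hypothesising that it will be a significant gain is another. Only the SAP does the second. A benefit reached by 12 months and held at 18 months is a good clinical result and supports the protocol's hypothesis in full, yet it does not satisfy the SAP's sentence as worded. With no decision rule, the same result could be reported as confirmation under the protocol and as partial confirmation under the SAP. The choice would be made after the data are seen.

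The extra contrast also takes a share of the significance level from the two comparisons that answer the study's question.

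**Working it through.** **Inputs.** Change 0.10, SD of change 0.25, 90% power, 5% level, divisor 3 (SAP 5). Two-sided paired t-test and minimum important change 0.03 (protocol 9). Enrolment 100 with 5 to 10% attrition (protocol 8.6.7), so at worst 100 × 0.90 = 90 completers.

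**Formula.** Power = P(|T| > t(1−α/2, n−1)), where T is noncentral t with n−1 degrees of freedom and noncentrality δ√n/σ.

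**1. The plan's own figures.** The smallest n with 90% power for δ = 0.10, σ = 0.25:
- α = 0.05: n = 68 (noncentrality 0.4 × √68 = 3.30), as stated.
- α = 0.05/3 = 0.0167: n = 88 (0.4 × √88 = 3.75), as stated.

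**2. A maintained benefit.** If the true 12-to-18-month change is zero, the chance of a significant result in the direction of gain is α/2. That is 0.0167/2 = 0.8% with the three-way correction, or 2.5% at 5%. A simulation of 20,000 trials (90 participants, gain of 0.165 at both post-implant visits, SD of change 0.25) gave 0.85% and 2.4%.

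**3. Power for the 12-to-18-month contrast, n = 90, α = 0.0167.** Only the SD of 0.25 stands in the documents, and there it is stated for the pre-to-post intervals. The smaller SDs are assumptions.

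| True gain | SD 0.25 | SD 0.20 | SD 0.15 | SD 0.12 | SD 0.10 |
|---|---|---|---|---|---|
| 0.03 | 10% | 16% | 30% | 48% | 66% |
| 0.05 | 30% | 48% | 76% | 93% | 99% |

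For a gain of 0.10 at SD 0.25 the power is 91%. For scale, 0.10 would be 0.10/0.165 = 61% of the 12-month change observed in the earlier dataset (protocol 9), in half the time.

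**4. Effect of the number of primary contrasts (δ = 0.10, SD 0.25).**

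| Primary set | α per test | n for 90% power | Power at n = 90 |
|---|---|---|---|
| Three pairs, Bonferroni | 0.0167 | 88 | 91% |
| Two pre-to-post pairs, Bonferroni | 0.025 | 81 | 93% |
| Two pre-to-post pairs, fixed order | 0.05 | 68 | 96% |

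The 96% applies to the first contrast, and to the second taken alone. If both true changes are 0.10, the chance that both are significant is at least 2 × 0.964 − 1 = 93%.

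**5. The model matters too.** If the plot looks close to linear, SAP 7.3 (Statistical Analyses) fits time as continuous. For means 0, 0.165 and 0.165 at months 0, 12 and 18, the mean time is 10, the centred times are −10, 2 and 8, and their squares sum to 168. The slope is 0.165 × (2 + 8)/168 = 0.00982 per month, so the fitted 12-to-18-month change is 6 × 0.00982 = 0.059 although the true change is zero. In the same simulation this was significant at 5% in practically every trial. With visit as a categorical factor this does not arise.

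**6. Precision of the estimate.** The 95% CI half-width at n = 90, SD 0.25 is 1.987 × 0.25/√90 = 0.052. To fall below 0.03, the SD must be under 0.03 × √90/1.987 = 0.143.

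**The case against.** Much can be said for the plan.

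- **The contrast is not new to the SAP.** Protocol 8.4 lists it under the primary end-point and section 9 repeats it. On the list of comparisons it is the synopsis that stands apart, so alignment could go either way. This stands. What is particular to the SAP is the claim of a gain.
- **A reader might infer that a stable benefit would make the study fail.** The documents do not support that. No success rule ties the contrasts together, and two positive pre-to-post results would still be reported as such. The point concerns the literal wording and the missing rule.
- **A reader might infer that the trial was sized only for the pre-to-post contrasts, or that it cannot detect a later gain.** Neither holds. SAP 5 recomputes the number for three pairs, and power for 0.10 is 91% on its inputs. What remains is that those inputs were stated for other intervals, and that power for 0.03 is low unless the 12-to-18-month SD is well below 0.25.
- **The cost in power is small.** With 90 to 95 completers the 88 is met, and 91%, 93% and 96% all exceed the 90% target. Bonferroni is offered as one method only; SAP 7.3 names Tukey comparisons. This stands, and it makes the matter one of interpretation more than of sample size.

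**Conclusion.** The inconsistency is real and should be resolved before analysis. The SAP hypothesises a second significant improvement that the protocol's hypothesis and synopsis do not contain, for an interval with no stated expected change or SD, and no rule says what confirms the hypothesis. If the benefit is maintained without growing, the literal SAP wording is met less than 1% of the time at 0.0167 with a pairwise or categorical-visit analysis. Under the continuous-time model the same plateau could instead be reported as a further gain.

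The size rests on 90 completers, a two-sided paired test and a Bonferroni level of 0.0167. The 10% power for 0.03 also rests on carrying the SD of 0.25 over to 12 to 18 months; across assumed SDs from 0.20 down to 0.10 it would be 16% to 66%. The consequence is an ambiguous primary conclusion. The chance of showing the pre-to-post benefit is not endangered.

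**What to change.** 1. In SAP 3, delete the parenthetical clause on 12 to 18 months from the primary hypothesis, so that it matches protocol 7.1.
2. Reconcile the synopsis, protocol 8.4, protocol 9 and SAP 3, 5 and 7.3 on which contrasts are primary.
3. State the decision rule: Pre1-Post1 first, then Pre1-Post2 only if the first is significant, each at two-sided 5%.
4. Keep Post1-Post2 as a secondary estimate with its 95% CI, from a mixed model with visit as a categorical factor (already the third option in SAP 7.3, Statistical Analyses). Do not attach a ±0.03 criterion for maintenance: at SD 0.25 the half-width of 0.052 means the interval could not fit inside those limits even with an observed change of zero.

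The cost is wording in both documents; enrolment and visits are unchanged. The downside is that a second improvement, if there is one, could be described with its interval but not claimed as a formal primary result. If the sponsor does want that claim, the SAP should keep it as a separate hypothesis with its own expected change and SD.

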Because all pairwise tests are of interest one method for undertaking this is to perform multiple tests and then adjust the significance level for the number of comparisons (in this case 3). This is equivalent to having a significance level of $0.05/3 = 0.0167$ and is a form of Bonferroni correction. If we recompute the sample size required with this significance level then at least 88 participants would be needed to find a change of 0.1 units in the HUI3 significant.

6. Study outcomes

The outcomes measures described in section 3 are detailed in the Protocol document and are briefly described here. This section could be updated when a better understanding of the distribution of the outcome measures is obtained through the data collected.

HUI 3

The HUI3 is a 15-item questionnaire. Responses to items are converted to levels and a scoring function applied. The ultimate result is a series of domain scores and a multi-attribute score. Domain scores typically don't have continuous distributions and need to be analysed with care. The multi-attribute score may be treated as continuous and is the focus of this study. Higher scores indicate less impairment.

CAP-II

The CAP-II comprises 9 questions placing each participant into one of 10 ordinal categories that determines their auditory performance at the time of assessment. Scores range from 0 (no awareness of environmental sounds or voice) through to 9 (use of telephone with unknown speaker in unpredictable context) so that higher scores imply better performance. These scores are an ordinal categorical scale and should not be treated as continuous.

SSQ

The SSQ is a 49-item questionnaire utilising a 10-point numerical rating scale for each question. The SSQ comprises three main subscales; speech perception (using the first 14 questions), spatial hearing (using the next 17 questions) and other qualities of hearing (using the last 18 questions).

Each subscale is the average of the scores from each subscale item; so, for example, scores on the speech component are between 0 and 10. These scores may be assumed to be continuous, higher scores imply better performance.

HHIE-S

The HHIE-S is a 10-item short form that assesses the impact of hearing impairment on emotional and social adjustment. Higher scores indicate greater handicap. The distribution is described as continuous.

Speech recognition in quiet

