3. Use visit as categorical variable. This essentially fits a linear model between time points but makes no assumption that the change from baseline is linear. Tukey pairwise comparisons between all pairs of time points (if time is found to be a significant predictor) are straight forward with this approach and should be undertaken using the *multcomp* package in R, which does not require balanced designs.

Secondary hypotheses analysis

The approach described for the primary hypothesis can be used for all continuous responses described in the secondary hypotheses. Failure of the assumptions may indicate that that a linear model is not appropriate and that other response distributions need to be explored. At this stage it is likely best that a statistician is consulted.

For ordinal responses such as the CAP II score an ordinal mixed-effects model including time as a fixed effect and participant as a random effect. The results of this model will show the

odds of being in a higher category compared to the current category over time (this interpretation is package dependent).

Tertiary hypotheses analysis

The approach described for the primary hypothesis is appropriate here also for continuous outcomes. As described above, for ordinal responses an ordinal mixed-effects model including time as a fixed effect and participant as a random effect. If the response variable is nominal (categorical without natural ordering) a multinomial mixed-effects model can be used and for binary responses a mixed effects logistic regression can be undertaken.

If only one pair of time points is of interest then for binary responses a test for the change in proportions can be undertaken and for continuous responses a paired t-test can be undertaken.

Analysis for other hypotheses

The other hypotheses involve the effect of covariates on a response and on the change over time. To assess the effect of a given covariate (for example age, gender, etc) the covariate can be added to the model as a fixed main effect in addition to the time variable and as an interaction with the time variable.

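### The Bonferroni and gated-Tukey corrections for the three linked HUI3 visit contrasts are stricter than a 5% family-wise error needs; a step-down rule would recover power at almost no cost

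*SAP*

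**What the plan says.** SAP section 3 defines the primary family as every pair among the three HUI3 assessments: pre-implant against 12 months, pre-implant against 18 months, and 12 against 18 months. The SAP's primary hypothesis also claims a further improvement from 12 to 18 months.

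SAP section 5 starts from one paired t-test: "a change of 0.1 with standard deviation of change equal to 0.25, would require 68 participants", at 90% power and 5% significance. Protocol section 9 has the same 68, with no adjustment. SAP section 5 then turns to the three contrasts: "Because all pairwise tests are of interest one method for undertaking this is to perform multiple tests and then adjust the significance level". It adds: "This is equivalent to having a significance level of $0.05/3 = 0.0167$ and is a form of Bonferroni correction". On that basis "at least 88 participants would be needed to find a change of 0.1 units in the HUI3 significant".

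For the analysis, the SAP section on statistical analyses offers Tukey differences as something that may be specified under a linear-time mixed model. If change over time is not linear, its third alternative treats visit as categorical and directs: "Tukey pairwise comparisons between all pairs of time points (if time is found to be a significant predictor"). The SAP section on multiple comparisons lists options (fewer analyses, a stricter level such as 0.01, or a Bonferroni-type adjustment) and fixes none of them. No section uses the dependence among the three contrasts.

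**The concern.** Write the three visit means as A (pre), B (12 months) and C (18 months). The null hypotheses are A=B, A=C and B=C. Any two of them imply the third, so exactly one cannot be false. Either all three are true, or at most one is. After one valid rejection, at most one true null remains, and it can be tested at the full 5% without raising the family-wise error above 5%. A penalty for three hypotheses on every contrast ignores this. The third alternative does so twice: with three visits, a significant overall test already protects the family, and Tukey then adds a second correction.

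What is at stake is power. It matters most for the 12-to-18-month change, which is part of the primary hypothesis and is probably the smallest of the three. SAP section 3 declares the same three contrasts of interest for the secondary tools, so the loss recurs there.

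**Working it through.** **Inputs.** From the SAP: change 0.10, SD of change 0.25, power 90%, alpha 0.05 or 0.05/3. From Protocol section 9: a two-sided paired t-test. From Protocol section 8.6.7: 100 enrolled and 5 to 10% attrition, so 90 to 95 evaluable. Not in either document, and therefore assumed and varied: the correlation r between the 12-month and 18-month changes, and the size of the 18-month change.

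**1. The plan's own figures.** Exact paired t-test, noncentrality (0.10/0.25)√n = 0.4√n:
- alpha 0.05: n=67 gives power 0.897 and n=68 gives 0.902, so 68.
- alpha 0.05/3: n=87 gives 0.899 and n=88 gives 0.903, so 88.

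Both are reproduced. Single-step Tukey for three means has critical value 2.364 (0.0192 per comparison), which gives n=85.

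**2. Two rules that use the link.**
- (a) Overall visit test at 5%; if significant, each contrast at 5%.
- (b) Smallest of the three p-values at 0.05/3; if significant, the other two at 0.05.

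**3. Family-wise error.** Simulated at n=90, SD 0.25, contrast-specific paired tests, r = 0.5 and 0.8:

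| True state | Bonferroni | Rule (a) | Rule (b) |
|---|---|---|---|
| No change at any visit | 4.2–4.4% | 5.0% | 4.2–4.4% |
| Only one null true, other changes 0.10 | 1.6–1.7% | 4.9–5.1% | 4.9–5.0% |

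Both rules hold 5% within simulation error.

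**4. Power for 12 to 18 months.** Take changes of 0.10 at 12 months and 0.15 at 18 months, n=90. The SD of the 12-to-18 change is 0.25√(2(1−r)), which is 0.25 at r=0.5 and 0.25√0.4 = 0.158 at r=0.8. The pre-to-18 contrast is rejected in 99.9% of trials, so under either rule the 12-to-18 contrast is in effect tested at 5% (critical value 1.99, against 2.44 for Bonferroni).
- r=0.5: noncentrality 0.05√90/0.25 = 1.90. Φ(1.90−2.44) is about 0.30; Φ(1.90−1.99) is about 0.47.
- r=0.8: noncentrality 0.05√90/0.158 = 3.00. Φ(3.00−2.44) is about 0.71; Φ(3.00−1.99) is about 0.84.

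Simulation gives the same: 30% to 47%, and 71% to 84%. Power for pre to 12 months rises from 91% to 96%.

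**5. N for 90% power on pre to 12 months (change 0.10), by simulation.**

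| 18-month change | r | Rule (b) | Rule (a) |
|---|---|---|---|
| 0.05 | 0.5 | 86 | 84 |
| 0.05 | 0.8 | 80 | 75 |
| 0.05 | 0.98 | 68 | 68 |
| 0.10 | 0.5 | 75 | 73 |
| 0.10 | 0.8 | 78 | 78 |
| 0.10 | 0.98 | 84 | 83 |
| 0.12 | 0.5 | 71 | 70 |
| 0.12 | 0.8 | 71 | 72 |

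The range is 68 to 86, below 88 throughout. Rule (b) rejects whatever Bonferroni rejects, so it can never need more than 88.

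**6. Which variance.** A model with only a participant random intercept uses one variance for all three contrasts: the average (1+1+2(1−r))/3 times 0.25². At r=0.8 that is 0.8 × 0.0625 = 0.05, an SD of 0.224 where the pre-to-12 contrast really has 0.25. A nominal 5% critical value of 1.97 then acts as 1.97 × 0.224/0.25 = 1.76, a true level of about 8%. Simulation of either rule on that model (A=B true, 18-month change 0.10, n=90) gives 5.0% at r=0.5, about 7% at 0.7, about 8% at 0.8 and above 9% at 0.9. With contrast-specific variances it stays at 5%.

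**The case against.** The strongest reply is that the SAP does not commit to the penalty. Section 5 calls Bonferroni one method, Tukey is optional under the linear-time model, and the multiple-comparisons section is a menu. That is largely right. A reader might infer that every route through the SAP over-corrects, and the text does not support this. Only the categorical-visit alternative is directive, and section 5 uses 0.05/3 for planning.

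A second reply is that under continuous linear time the three contrasts are multiples of one slope. There is then one hypothesis and nothing to step down. This also stands.

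Third, the lost power does buy something: when one null is true, Bonferroni's error is 1.6 to 1.7%, not 5%. True, but the SAP sets itself 5%.

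Fourth, Tukey gives matching simultaneous intervals and the step-down rules do not. This is a real cost, which reporting Tukey intervals alongside reduces.

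Finally, nothing changes in recruitment. With 90 to 95 evaluable, Bonferroni power for a change of 0.10 is already 91 to 93%, and Protocol section 9 ties the 100 to the single HUI3 domains, not to the 88.

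**Conclusion.** The point holds as an inexpensive gain in efficiency. For the three linked contrasts with visit as categorical, Bonferroni at 0.05/3, and Tukey after a significant time effect, demand more than 5% family-wise control needs. The gain is 13 to 17 percentage points of power for the 12-to-18-month contrast in the scenarios shown and about 5 points for pre to 12 months. The exact size depends on the correlation and the 18-month change, which the documents do not give.

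Three stronger readings should be resisted:
- The 88 is not wrong. It is exact for its stated method and does not depend on the correlation.
- No single smaller figure can replace it. A value near 75 needs equal changes of 0.10 and a correlation of about 0.5; the range is about 68 to 86.
- The two rules are not interchangeable. Both hold 5%, but they are different procedures with slightly different N, and neither is safe on the pooled variance of a random-intercept model.

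**What to change.** In SAP section 5 and in the section on statistical analyses, for the HUI3 multi-attribute score:

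1. Treat visit as categorical and pre-specify one rule: either (a) an overall visit test at 5%, then each of the three contrasts at 5%; or (b) the smallest p-value at 0.05/3, then the other two at 0.05. Remove Tukey as the decision rule after a significant time effect.
2. Use contrast-specific variances, from paired tests or a mixed model with unstructured visit covariance. The unstructured model keeps the SAP's aim of using all available data.
3. Keep the 88 as the Bonferroni figure. Beside it, state the N under the chosen rule with its assumed correlation and 18-month change (for example 73 to 78 for equal changes of 0.10 and r from 0.5 to 0.8).
4. Report Tukey intervals alongside if simultaneous intervals are wanted. The same rule can serve within each continuous secondary tool.

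The cost is a few sentences and one change of covariance structure, with no new data, visits or enrolment. The drawback is that decisions will not always match the simultaneous intervals. If the sponsor keeps linear time, the SAP should say that there is one slope to test and drop the three-way correction.
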